In the list of *, use a row for an adverse reaction; enter multiple adverse reactions in the equivalent number of rows for a patient. Entry of a patient number, etc. should be repeated.

4) Table for “Patients in the efficacy analysis group”

A table and a chart of changes in HIV-RNA load/CD4	
Prepare a chart and table on the changes in HIV-RNA load/CD4 in patients with and without treatment history, with and without concomitant CYP3A inhibitors, sex, with and without complications, with and without concomitant drugs, CDC classification and for all patients in the efficacy analysis group.
 
Pre-administration (Month 0) should be the most recent date within 30 days before administration including the first administration date.
 
For post-administration (Month 3, 6, 9, etc.), choose the value obtained on the most recent date within ±45 days from each point of Month 3, 6, 9, etc. If a “test value” is missing either before or after administrations, it should not be included in the chart.
 
Use a line chart with test values on the y-axis and months after administration (for every 3 months) on the x-axis.
 
For each point, extend the whisker in a single direction to show the SD value.
 
When you have n=1 for each point, display it with a dot without connecting it with a line.
 
Of note, for the maximum number of HIV-RNA copies detected, replace it with 399 from the initiation of survey to March, 2008, with 39 from April, 2008 to 2010 and with 19 in and after 2011 (depends on the site). Handle the encoded values, etc. as follows: Replace the values with inequality sign with the following [1] to [3] in calculation:

--	--

	
[1] <400: The value that you subtract 1 from the figure without inequality sign. Note that the inequality sign must be removed from the figures with inequality sign. For example: change "<20" to "19", "<40" to "39", "≤20" to "20", "≤40" to "40"
 
[2] ≥400 and <100000: Missing
 
[3] ≥100000: the value without inequality sign. For integer values less than 400 with no inequality sign, use them as they are without replacement.

Patients included in the chart [data in each plot]	Display the patient registration numbers and test results for each point of Month 0, 3, 6, 9, etc. to the number of HIV-RNA copies and CD4, the output data in the above graph.

5) Changes in tropism

For the patients who underwent a tropism assay (the patients whose tropism had been classified when the administration was started), prepare a list of their tropism assay results obtained within ±45 days of each point at Month 3, 6, 9, etc. of administration.

NOTE: These table forms may be subject to change due to the aggregated results or the relevant system.

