DRUG USE INVESTIGATION FOR HIV INFECTION PATIENTS OF MARAVIROC

- HRD Joint Survey -

STATISTICAL ANALYSIS PLAN

CELSENTRI Tablets 150 mg Statistical Analysis Plan

Outsourced by
Product name
Pregnant Women
Prepared by

ViiV Healthcare K.K.
CELSENTRI Tablets 150 mg Drug Use Survey, Special Drug Use Survey for
CMIC-PMS Co., Ltd. PPD

<General Definitions>

Re-examination period	
Number of report	Survey period
1st	2008/12/25 (H20) - 2009/2/5
2nd	2/6/2009 (H21) - 8/5/2009
3rd	8/6/2009 (H21) - 2/5/2010
4th	2/6/2010 (H22) - 8/5/2010
5th	8/6/2010 (H22) - 8/5/2011
6th	8/6/2011 (H23) - 8/5/2012
7th	8/6/2012 (H24) - 8/5/2013
8th	8/6/2013 (H25) - 8/5/2014
9th	8/6/2014 (H26) - 8/5/2015
10th	8/6/2015 (H27) - 8/5/2016
11th	8/6/2016 (H28) - 8/5/2017
12th	8/6/2017 (H29) - 8/5/2018
13th	8/6/2018 (H30) - 12/24/2018
Re-examination	12/25/2008 (H20) - 12/24/2018
Date conversion	
When you calculate dates for aggregation, make the following replacement: Replace the date “AA=early in the month” with 05, “BB=middle of the month” with 15, “CC=late in the month” with 25, and “DD=around” with 01. Replace “20EEEEEE=continued” with “the outcome confirmation date of the patient”. If nothing is provided, enter “entry date”. The new survey does not have entries of 20EEEEEE, but enter 20EEEEEE for continued administration if “entry date” is found. When you need to replace any inappropriate date (such as Day 00), add the following process: When the date in “first administration date” is not appropriate as a date, choose the final date of the month. When the month and date in “first administration date” are not appropriate as a date, enter “1231”. When the date in “final administration date” is not appropriate as a date, enter “01”. When the date in “onset date of adverse event” is not appropriate, enter “01”. When the date in “laboratory test date” is “00” or “99”, enter “01”. Only a date after the approval date (=December 25, 2008) should be used for CELSENTRI Tablets (when the first administration date comes before the approval date, replace it with the approval date).

Date unit	A week has 7 days, a month has 30 days, and 1 year has 365 days.
Prior to administration	It should be within 30 days prior to the first administration of CELSENTRI Tablets and be the closest date to the first administration date (the administration date is also included).
Displayed digit	Decimal numbers should be rounded to the second decimal place.

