Missing data	When aggregating “unknown” and “not provided”, count them collectively as “unknown/not provided”. Of note, separate “unknown” and “not provided” for “medical history” and “allergy history”.

MedDRA	Use MedDRA/J Version 21.0. Count PTs for aggregation and use primary for SOC.
Adverse events	Adverse events for which the “relationship” column with CELSENTRI Tablets is not checked or “no relationship” is checked among the events that occurred on or after the first administration date of the drug, plus, the adverse reactions that are defined below. But the decision is based on the ViiV Healthcare’s company assessment. Of note, they also include the event for which you can’t decide whether it occurred on the first administration date of CELSENTRI Tablets because of unknown date even after <General Definitions> “Date conversion” resulting from its inarticulate onset date. Overlapped events with the same PT in a patient should be counted as one event in accordance with <General Definitions> “Integration process”.
Adverse reactions	The events for which the relationship with CELSENTRI Tablets cannot be ruled out. The decision is based on ViiV Healthcare K.K.’s company assessment.
Serious adverse events	“Serious” events in the seriousness criteria among the above “adverse events”. The decision is based on ViiV Healthcare K.K.’s company assessment.
Co-administration	Co-administration refers to a drug concomitantly used for at least a day. Of note, if only one date is overlapped when two anti-HIV drugs are used on the same day (as the first administration for one and the final administration for the other), it should be regarded as “replacement” and not counted as a concomitant drug.
Integration process	Take the following integration process per PT.
	<When the events occurred on the same date>
[Seriousness]	Integrate into a more severe event.
[Relationship]	The same years: Integrate into the final year when the relationship was observed. Different years: Integrate into the final year.
[Outcome (outcome confirmation date)]	The same year: Death>Not recovered>Recovered with sequela>Unknown>Recovering>Recovered>Not provided Different years: Integrate into the final year.
	Of note, when the onset date is unknown or not provided, the event with the onset date should be selected.
	<When the events occurred on different dates>
[Onset date]	Select the initial onset date.
[Seriousness]	Integrate into a more severe event.

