Age	Calculate the Western-style age as of the initial administration date of CELSENTRI Tablets based on the date of birth. Of note, if the description only includes the year for date of birth in a site, describe it as "January 1". If it only includes the year and the month, replace it with "the first date of the month". If a "period of age" or "age" is provided in the "date of birth" column, select the "period of age" or "age" provided in the CRF when the patient was started on CELSENTRI Tablets only after confirmation that it is the data for the applicable year. [Stratification] [1] ≤14 years old, ≥15 and ≤64 years old, ≥65 years old, unknown/not provided [2] ≤9 years old, ≥10 and ≤19 years old, ≥20 and ≤29 years old, ≥30 and ≤39 years old, ≥40 and ≤49 years old, ≥50 and ≤59 years old, ≥60 and ≤69 years old, ≥70 years old, unknown/not provided
Inpatient/outpatient classification	Use the value in the CRF at the first administration of CELSENTRI Tablets. [Stratification] inpatient, outpatient, inpatient
Treatment history for HIV infection	Use the value in the CRF at the first administration of CELSENTRI Tablets. However, if an anti-HIV drug is administered prior to the initiation of CELSENTRI Tablets, select "2=present". [Stratification] Absence, Presence, Unknown/not provided
Race	Use the value in the CRF at the first administration of CELSENTRI Tablets. [Stratification] Japanese, others, unknown/not provided
Route of infection	Use the value in the CRF at the first administration of CELSENTRI Tablets. <Multiple-answers are acceptable in this column> [Stratification] Blood product, Mother-to-child transmission, Medical accident, Sexual transmission, Others, Unknown/not provided
Duration of disease	Calculate the years from infection to the first administration date. Display the minimum and the maximum as well. [Stratification] ≤1 year, >1 year and ≤2 years, >2 years and ≤3 years, >3 years and ≤4 years, ≥5 years, unknown/not provided
Medical history	Use the value in the CRF at the first administration of CELSENTRI Tablets. If there is an event that both occurred and recovered before the first administration of CELSENTRI Tablets in the 'adverse event' column, regard it as "present". [Stratification] Absence, Presence, Unknown/not provided
Presence/absence of allergy	Use the presence/absence of allergy provided in the CRF at the first administration of CELSENTRI Tablets. [Stratification] Absence, Presence, Unknown/not provided

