Complications	Use the complications provided in the CRF at the first administration of CELSENTRI Tablets. The events that occurred and did not recover before the first administration of CELSENTRI Tablets in the 'adverse event' column. [Stratification] Absence, Presence, Unknown/not provided
Type of complications	Complications provided in the CRF at the first administration of CELSENTRI Tablets <Multiple-answers are acceptable in this column> In addition, reflect the ViiV Healthcare K.K.'s instruction for data amendment. [Stratification] • "Haemophilia": complications are present "1. Haemophilia"

	
•"Liver disorder": the disease selected as liver disorder in 'complication is present': 3. Hepatitis A", "4. Hepatitis B", "5. Hepatitis C", "6. Other liver disorders", or "8. Others"

The mean daily dose	
The mean dose for "administration period" Even if "administration period" is unknown, the provided value should be regarded as the mean when there is no change in "the dose". [Stratification] >minimum and < 2 tablets, 2 tablets, >2 tablets and <maximum, unknown/not provided

Dosing frequency	
Calculate the number of dosing in a day. [Stratification] 1, 2, ≥3 and ≤maximum, unknown/not provided

Administration period	
\sum (final administration date - first administration date+1). Exclude the washout period. [Stratification] ≤180 days, >180 and ≤365 日、 >365 and ≤730 日、 >730, unknown/not provided

Administration period <cumulative>	
Count "the number of patients" by accumulating "administration period", count "the number of patients with adverse reactions" based on the "administration period" until the first adverse reaction occurred, and count "the number of adverse reactions" based on the "administration period" until the applicable adverse reaction occurred. Exclude the washout period. [Stratification] ≤180 days, >180 and ≤365 日、 >365 and ≤730 日、 >730, unknown/not provided

Total dose	
\sum {(Final administration date - First administration date+1) × a daily dose}. Exclude the washout period.[Stratification]≤360 tablets, >360 tablets and ≤730 tablets, >730 tablets and ≤1460 tablets, >1460 tablets, unknown/not provided

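### Invalid-day rules place the first dose late but adverse event onset and last dose early, which can misdate early not-related events, shorten exposure below zero and make an on-drug value the Month 0 baseline

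*SAP*

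**What the plan says.** All the date rules are in the SAP, General Definitions, Date conversion. They apply when a day is unusable, not when it carries a code for early, middle or late in the month.

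- First dose: "When the date in “first administration date” is not appropriate as a date, choose the final date of the month". If the month is unusable too, the date becomes 31 December.
- Last dose: "When the date in “final administration date” is not appropriate as a date, enter “01".
- Adverse event onset: "When the date in “onset date of adverse event” is not appropriate, enter “01".

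Three later rules use these dates.

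- **Adverse events (General Definitions).** Not-related or unchecked events count only "among the events that occurred on or after the first administration date of the drug". Adverse reactions are added with no date condition. An exception keeps events whose timing is still undecidable after conversion, "resulting from its inarticulate onset date".
- **Administration period (Handling of items).** This is the sum of last date minus first date plus 1. It has no lower limit and no check that the last date follows the first. Total dose is built the same way.
- **Month 0 (Type of Tables, 4).** This is the most recent value in the 30 days up to and including the first administration date.

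Under Preliminary process [3], every event dated before first dose, whatever its assessed relationship, is listed for the sponsor to decide whether to reclassify it as medical history or a complication.

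**The concern.** Each rule picks an extreme, and the extremes point in opposite directions: the start of treatment as late as possible, its end and event onsets as early as possible. Three kinds of output are exposed.

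- **Early adverse events.** A not-related event in the month of first dose can be dated before treatment and leave the adverse event and serious adverse event tables, including Attachment Form 2-2/10. The priority items in protocol 7.10 are adverse events tabulated by causal relationship, so not-related events matter there too. Unless restored, such an event also fits the SAP wording for medical history ("If there is an event that both occurred and recovered before the first administration of CELSENTRI Tablets") or complications ("The events that occurred and did not recover before the first administration of CELSENTRI Tablets"). Both are background factors in the adverse reaction incidence table.
- **Exposure.** Administration period and total dose are also factors in that table. Both are biased downwards, and the period can be zero or negative, in which case it falls in the lowest stratum.
- **Baseline.** If the first dose is moved later, values taken on treatment qualify as Month 0, and taking the most recent value prefers them.

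**Working it through.** The documents give no figure to reproduce, so the rules were applied by enumeration. The assumptions are mine: equally likely days, a 30-day month, and calendar start dates in 2010 where stated.

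**(a) Adverse events in the month of first dose.** Let d be the true first-dose day and a the true onset day, with a ≥ d.
- Pairs: 30 × 31 / 2 = 465.
- Onset day invalid (set to 01): dated before dose if d > 1, which is 465 − 30 = 435.
- First-dose day invalid (set to 30): dated before dose if a < 30, which is also 465 − 30 = 435.
- Both invalid: 01 is before 30 in all 465.

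With onset spread evenly over the first year on drug, the shares are 435 / (30 × 365) = 4.0% with one invalid day and 465 / (30 × 365) = 4.2% with both. For a year-only start (31 December), 66,795 − 365 = 66,430 same-year pairs are dated before dose. That is 66,430 / (365 × 365) = 49.9% of events in the first 365 days.

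The exception for undecidable timing does not help. An onset already set to 01 is no longer unknown, and a fully recorded onset compared with a converted first dose is not an onset-date problem.

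**(b) Administration period.** Period = last − first + 1.
- Both days invalid in the same 31-day month: 1 − 31 + 1 = −29 days.
- Mean error with both invalid in different 30-day months: −14.5 − 14.5 = −29 days, range −58 to 0. It is never positive.
- Example: 1 January to 31 July 2010 is 212 days. With both days invalid it runs from 31 January to 1 July, 152 days, and moves from the 181–365 stratum to ≤180.

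| Both days invalid, every 2010 start | Result |
|---|---|
| Period zero or negative: true 14, 28, 42 days | 57%, 11%, 0% |
| Stratum too low: true 195, 205, 220 days | 62%, 29%, 0% |

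With true lengths assumed uniform on 1–1095 days, the stratum is too low for 4.6% of courses with both days invalid, 4.0% with one, and 46% with a year-only start and a valid stop date.

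**(c) Month 0.** Suppose values exist on the first-dose day d and next k days later, and the first dose is set to day 30. The on-drug value is chosen if d + k ≤ 30, so in (30 − k)/30 of cases: 23/30 for k = 7, 16/30 for k = 14, and 0 for k ≥ 30.

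True baselines are lost as well. With one value taken 0 to 30 days before dosing there are 30 × 31 = 930 combinations. The shifted window keeps 495 and drops 435. For a year-only start the window is 1–31 December, and it lies wholly on drug for true starts up to 30 November, 334 of 365 days.

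**The case against.** The strongest reply is that the sponsor sees these events. Adverse events are settled by company assessment after a matching step whose specification is not in the documents. Preliminary process [3] lists the pre-dose events, with a separate sheet for unknown onset dates. This stands in part: the shares in (a) are losses before review, and what remains afterwards cannot be known. But no criterion for converted dates is stated, and that review does not cover exposure or Month 0.

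Invalid dates may also be few. Protocol 5.2 requires the start date at enrolment, protocol 5.4 provides for reinvestigation, and a patient continuing treatment takes the outcome confirmation date as the end. Negative values would show in the printed minimum period and in days to onset. All of this stands and limits the severity. A period that is too short but positive would still look normal. So would an on-drug Month 0, because the listing of plotted data asks for patient numbers and results, not dates. The Month 0 effect also depends on test spacing, which the documents do not give, and vanishes at 30 days or more.

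A reader might infer that the primary adverse reaction count is biased because reactions drop out. The documents do not support that: the date condition does not apply to adverse reactions. Nor are they untouched. They can become medical-history or complication candidates, and their days to onset and cumulative period and dose rows use the same dates.

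A reader might also infer that unknown test days give a second route to an on-drug Month 0. The SAP does not say whether its laboratory-date rule covers HIV-RNA and CD4, and protocol 7.7 and 7.8 list these apart from the laboratory panel, so nothing here rests on it.

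**Conclusion.** The point holds as a modest defect. As written, the rules can date on-treatment not-related events before dosing, give periods of zero or less, and take an on-drug value as Month 0. Every percentage is conditional on a date being invalid and on the assumed distributions. The documents do not allow an estimate of the overall effect on the survey.

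The statement that exposure can only be understated is limited to the invalid-day rules. Another conversion can lengthen a period: a first dose coded as around a date is set to 01. The approval-date rule ("when the first administration date comes before the approval date, replace it with the approval date") also moves first doses later, but it is separate and should be raised separately.

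**What to change.** 1. **Adverse events.** Count a not-related or unchecked event, with a flag, whenever its partial onset date or the partial first-dose date is compatible with onset on or after first dose. Leave recorded onset dates unchanged, and show days to onset as unknown if either date is partial. Cost: some flagged events will be pre-treatment, up to 435/900 (48%) of start-month events with an invalid day and about half of start-year events for year-only starts.
2. **Exposure.** Require the last date to be on or after the first, with a period of at least one day, and use one rule at both ends for the printed value, for example the SAP's own day 15. This alone does not settle the strata: with both days invalid it puts 3.7% of courses too high, against 4.6% too low now. So flag courses whose shortest and longest possible periods fall in different strata, and report them in a sensitivity analysis. Moving them to unknown/not provided is optional. It would affect about 13% of courses with both days invalid, 8% with one and 79% of year-only starts, and the SAP excludes unknowns from tests.
3. **Month 0.** For an invalid first-dose day, anchor the 30-day window on day 01 of the month and accept only values on or before that date. This keeps 495/930 single baselines, the same number as now, and none is on drug. The anchor must be stated: with the same acceptance limit, day 15 would keep 390 and month end 60. For year-only starts, set Month 0 to missing unless other records bound the start. Say whether the laboratory-date rule covers HIV-RNA and CD4.
4. **Reporting.** Give the number of converted dates by field, and how many adverse events, serious adverse events, strata and Month 0 values change against the present rule.

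The work is SAP wording and reprogramming of the date conversion. No new data are needed.

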DRUG USE INVESTIGATION FOR HIV INFECTION PATIENTS OF MARAVIROC

- HRD Joint Survey -

NON-INTERVENTIONAL (NI) STUDY PROTOCOL

Drug Use-results Survey of Celsentri Tablets 150 mg – HRD Cooperative investigation – Protocol

1. Objectives

To understand the following matters and to examine whether or not a special drug use-results survey and/or postmarketing clinical study is needed:

- Unknown adverse drug reactions (ADRs)
- Occurrence of ADRs under actual conditions of use
- Factors that are likely to affect safety, efficacy and other relevant matters

In addition, effects on immune competence, liver function and the cardiovascular system will be also evaluated as priority investigation items.

2. Planned Sample Size of the Survey and Rationale of Determination

Based on an approval condition, the drug use-results survey of Celsentri will be conducted in all patients treated with this drug at survey sites to the extent possible.

For the drug use-results survey implemented as part of the HRD cooperative investigation in which Celsentri is included, however, consideration will be paid by setting the upper limit of the number of patients to be enrolled at sites where there are many survey subjects for eliminating the influence of the present survey on routine medical practice at the sites and maintaining the quality of the survey due to this acute increase in the number of patients. When paying consideration, approximately 40 patients per investigator should be enrolled in the HRD cooperative investigation while taking account of time points for collecting case report forms (CRFs) and for case review by the investigator. If it is necessary of select subjects from all patients, consideration should be given so that there is no arbitrarily bias in efficacy or safety.

3. Subjects

The indication of Celsentri is as follows:

CCR5-tropic HIV-1 infection

The subjects of this survey will be patients who are prescribed with Celsentri (including retrospective patients).

4. Planned Number of Survey Sites by Medical Department

Institutions with which many physicians with a lot of experience in treatment are affiliated and which have many target patients (27 sites; Appendix 1).

5. Methods

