Attachment Form 2	Display the aggregation results of adverse reactions in <General Definitions> in accordance with the Safety Periodical Report Green Book. Overlapped adverse reactions with the same adverse reaction name (PT) in a patient should be counted as one event in accordance with <General Definitions> “Integration process”. Display the columns of “Cumulative results in Drug Use Result Survey” and “Total” only per “Survey period” provided in <General Definitions>. Leave the ‘status until approval’ column blank. Display System Organ Class (SOC) in the order of the international agreement and Preferred Terms in the order of encoded PTs.
Attachment Form 2-2 (Attachment Form 10 as the re-examination application document)	Display the aggregation results of serious adverse events in <General Definitions> in accordance with the Safety Periodical Report Green Book. Overlapped adverse events with the same adverse event name (PT) in a patient should be counted as one event in accordance with <General Definitions> “Integration process”. Display the columns of “Cumulative results” and “Total” only per “Survey period” provided in <General Definitions>. Leave the ‘status until approval’ column blank. Display System Organ Class (SOC) in the order of the international agreement and Preferred Terms in the order of encoded PTs. *Aggregate it with the number of patients in the special drug use survey for pregnant women.
*A list of adverse events	Prepare a list for adverse events in <General Definitions>. © Displayed items: [1] patient number, [2]repeat, [3] adverse event name (the reported name, and each code and the name of SOC, PT and LLT), [4] seriousness (company assessment, physician’s assessment), [5] expected/unexpected, [6] the first administration date of CELSENTRI Tablets, [7] the onset date, [8] days to the onset, [9] outcome, [10] relationship with CELSENTRI, [11] pediatrics (calculated), the elderly (calculated), renal disorder (calculated), liver disorder (calculated), pregnant women (calculated), each flag of haemophilia (calculated), male/female patient, patient’s age

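### Moving a pre-approval first dose to 25 December 2008 can make the Month 0 HIV-RNA/CD4 value an on-treatment value and shortens recorded onset times for those patients

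*SAP*

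**What the plan says.** The Date conversion entry in the SAP's General Definitions opens with "When you calculate dates for aggregation, make the following replacement". For this product it adds "Only a date after the approval date (=December 25, 2008) should be used for CELSENTRI Tablets", with the instruction that "when the first administration date comes before the approval date, replace it with the approval date".

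Several other definitions then depend on the first administration date:

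- **Prior to administration** (General Definitions): "It should be within 30 days prior to the first administration of CELSENTRI Tablets and be the closest date to the first administration date". The pre-administration CDC class in Handling of items uses the same window.
- **Efficacy tables and charts** (Type of Tables, 4): "Pre-administration (Month 0) should be the most recent date within 30 days before administration including the first administration date". For later points the instruction is to "choose the value obtained on the most recent date within ±45 days from each point of Month 3, 6, 9, etc". A patient lacking a value before or after administration is left out of the chart.
- **Safety:** the adverse event list shows days to onset beside the first administration date. The administration period runs from that date. First adverse reactions are tabulated in classes of up to 180, 365 and 730 days, and beyond.

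Under Handling of cases, the safety exclusion for non-administration removes only patients with no traceable use since approval. The two efficacy exclusions concern off-indication use and absent CD4 or RNA data. A pre-approval starter who continued therefore stays in both sets. Neither document flags or counts these patients, or plans an analysis without them.

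**The concern.** A rule that fits a regulatory counting period is also being used to define a treatment baseline. For a patient already taking the drug, the converted date is not the start of treatment, so a value labelled as pre-administration may have been taken on treatment.

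Protocol 8.2 aims to find factors that affect efficacy and the onset of adverse reactions. For the affected patients, both the baseline and the time axis used for that purpose would be mislabelled. A reader of the tables could not tell, because the converted date replaces the true one and no flag is planned.

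**Working it through.** The plan gives no figure tied to this rule, so there is none to reproduce. The check applies the SAP's own date rules.

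**Inputs from the SAP:** approval on 25 December 2008; Month 0 window of 30 days up to and including the first administration date; a month of 30 days; onset classes cut at 180, 365 and 730 days.

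**Inputs assumed because the documents do not give them:** L, the days from true first dose to approval; f, the share of charted patients who started before approval; r, the share of their response already reached at the recorded Month 0.

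**1. Month 0 window.** The converted start is 25 December 2008, so the window is 25 November to 25 December 2008, or 31 calendar days. With continuous use, the number of window days after the true first dose is the smaller of L and 31.

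| L (days) | True first dose | Window days after first dose |
|---|---|---|
| 5 | 20 Dec 2008 | 5 of 31 |
| 10 | 15 Dec 2008 | 10 of 31 |
| 20 | 5 Dec 2008 | 20 of 31 |
| 30 | 25 Nov 2008 | 30 of 31 |
| 31 or more | 24 Nov 2008 or earlier | 31 of 31 |

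From L = 31 upward, any Month 0 value is on treatment. For L from 1 to 30, the rule takes the latest value in the window. Month 0 is then on treatment if any test followed the first dose, and a true baseline otherwise. A patient with no value in the window has no Month 0 and drops out of the chart.

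**2. Visit points.** True day of the nominal Month 3 point = 90 + L. This gives day 120 for L = 30, day 180 for L = 90 and day 270 for L = 180. Months 6, 9 and so on move by the same L.

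**3. Days to onset.** Recorded day = true day − L. For a reaction on true day 200, which belongs in the class above 180 and up to 365 days:

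- L = 20: 200 − 20 = 180, now in the class up to 180 days
- L = 90: 200 − 90 = 110, same shift
- L = 180: 200 − 180 = 20, same shift
- L = 365: 200 − 365 = −165, which is before the converted first dose

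**4. Effect on the group mean change.** Suppose all patients share a true mean change Δ. Then the observed change = (1 − f)Δ + f(1 − r)Δ = Δ(1 − f·r).

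| f | Share of true change shown, r = 1 | r = 0.25 |
|---|---|---|
| 1% | 99.0% | 99.8% |
| 5% | 95.0% | 98.8% |
| 10% | 90.0% | 97.5% |
| 20% | 80.0% | 95.0% |

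**5. With the true first dose as anchor,** L = 0. Month 0 is a value from the 30 days up to the real start, or is missing, and Month 3 is true day 90. Leaving pre-approval starters out of the chart sets f = 0 and removes the dilution.

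**The case against.** The strongest reply is that the rule may be a guard clause that touches few patients or none. Neither document counts pre-approval starters, and enrolment ran from April 2009 to March 2017 (Protocol 6). This stands, and it limits the size of the effect. It does not make the label right for any patient who is affected.

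The second reply is that 25 December 2008 is also the first day of the re-examination period, so starting safety follow-up there is coherent. This also stands for counting events and exposure. It gives no reason to use the same date as the efficacy baseline.

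Three stronger readings are tempting, and the documents do not support them:

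- **That early adverse reaction risk is understated.** The SAP's definition of adverse reactions has no onset-date limit. Events before the first administration date are only candidates for reclassification as history or complications, on the sponsor's instruction. Shortened onset days can also move later reactions into the earliest class, so the net direction is unknown.
- **That the protocol's subjects are known to include pre-approval users.** Protocol 3 admits patients "including retrospective patients", but someone who started after approval and before the site contract is also retrospective and keeps the true date. The phrase shows only that pre-approval starters are not excluded.
- **That Month 0 is on treatment for every pre-approval starter.** This is certain only for a first dose at least 31 days before approval with continuous use.

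Tropism is a weaker example than CDC class. Its window already extends 30 days after the first administration, so treated values are allowed for everyone.

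**Conclusion.** The point holds for the baseline and the time axis. For continuous users who started on or before 24 November 2008, any Month 0 HIV-RNA or CD4 value is an on-treatment value. For starts from 25 November to 24 December 2008, it may be. Their change from Month 0 is pulled toward zero to the extent that the response came before approval. Their visit points move by L days, and their pre-administration CDC class may be a treated value. Days to onset are short by exactly L, with no established direction of bias in adverse reaction risk.

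The effect on group figures depends on an unknown share. The mean change loses at most 1% at a 1% share and 5% at a 5% share, and less if the response was incomplete by the recorded Month 0. These bounds assume the same true mean change in both groups and a Month 0 value in the window for each charted patient. If few patients are affected, the effect on group figures is small, although the individual baselines remain mislabelled.

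**What to change.** In the Date conversion entry, limit the replacement to safety counting and exposure, where the 25 December 2008 start can stay. Then:

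- Keep the true first administration date for Month 0, the Month 3, 6, 9 windows and pre-administration background.
- Add a flag for patients whose true first dose precedes approval, and report their number.
- Leave flagged patients out of the Month 0-based HIV-RNA/CD4 charts and tables unless a true pre-treatment value is available.
- Show the days-to-onset tables with and without flagged patients. Keep them on the approval-date clock used for the cumulative administration-period tables, so that patients and reactions are not classified on two different clocks. State in a footnote that onset days for flagged patients exclude pre-approval use.

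The cost is a change of SAP wording, one derived flag and a slightly smaller efficacy n. The remaining limitation is that safety results still leave out time on drug before approval, which should be stated in the report.
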